4.0 STUDY PURPOSE

The purpose of this study is to assess the safety and effectiveness of BLVR using the Pulmonx Endobronchial Valve (EBV) in treated study participants compared to control participants to support a premarket approval application to FDA.

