7.5 Crossover of Control Study Participants

After completing the 1-year visit, a control arm participant may be permitted to crossover to the study treatment if (s)he continues to qualify for the study treatment. In order to qualify for crossover, a control arm participant must have been followed up successfully through 1 year and demonstrate lack of a clinically important response. The crossover procedure must be scheduled to occur within the 60 days after the 1 year visit. After treatment, the follow-up visits and testing at each visit will be identical to the study schedule for treatment arm participants.

Note: Per Revision H of this protocol, the requirement of a heterogeneity score of 15% between lobes is not applicable for any remaining crossover subjects. The most diseased target can be treated regardless of heterogeneity, provided that the target lobe is collateral ventilation negative (CV-).

Patients treated after approval of this Amendment will fall outside of the original 60 day window from the 1-year visit date. This delay will not be marked as a deviation from the protocol.

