21.0 REGULATORY AND REPORTING REQUIREMENTS

21.1 Adverse Events and Reporting

An adverse event (AE) is an untoward medical occurrence in a patient or clinical investigation participant receiving a procedure using a medical device and that does not necessarily have a causal relationship with the treatment. An adverse event can therefore be any unfavorable and unintended sign (including an abnormal laboratory finding), symptom, or disease temporally associated with the use of a medical device, whether or not related to the medical device. Generally, a condition is an adverse event if it is undesirable and was not present before the participant underwent the procedure or is more severe than before the participant underwent the procedure, and/or is more frequent than before the participant underwent the procedure.

Adverse event information will be collected over the entire duration of the study. Collection of adverse event data will commence upon random assignment of a study participant. The following information will be recorded on the appropriate case report form:

- Event diagnosis or syndrome
- Date of onset
- Duration
- Severity (mild, moderate, or severe)
- Relationship to the device (not related, possibly related, probably related, related, or unknown)
- Relationship to the procedure (not related, possibly related, probably related, related, or unknown)
- Action taken, and
- Outcome (not resolved, resolved with sequelae, or resolved).

If the diagnosis or syndrome is not known, the unfavorable or unintended sign or symptom experienced by the participant should be recorded on the CRF. Adverse events will be determined by the study investigator treating the study subject. Adverse events will be monitored and treated as appropriate until the event has subsided or, in case of permanent impairment, until the event stabilizes and the overall clinical outcome has been ascertained. Adverse events will be followed until resolution or until the end of the study. In addition, all IRB and FDA reporting requirements will be followed.

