21.2 Serious Adverse Events and Reporting

A serious adverse event (SAE) is any untoward medical occurrence that:

- Results in death,
- Is life-threatening,
- Requires inpatient hospitalization or prolongation of existing hospitalization, or
- Results in persistent or significant disability/incapacity, or congenital

anomaly/birth defect.

All serious adverse events should be reported immediately (within 24 hours of knowledge of the event) to the study sponsor. All IRB and FDA reporting requirements will be followed.

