inter-lobar fissures	percent complete	percentage of participants

V. Adjustment for Potential Confounders

The covariates shown in Table 6 may be potentially influential with respect to the effectiveness endpoints. If any of these covariates are found to be out of balance between the groups (at the two-sided 0.10 level), they will be included in a multivariate analysis, along with an indicator of treatment group, to evaluate their potential effect on the study conclusions. A multivariate logistic regression model will be used for primary and secondary endpoints.

Table 6. Covariates

	Baseline	Procedure
Gender	X	
Age	X	
Clinical Site	X	
6MWD	X	
Patient-reported health status measures (e.g. SGRQ)	X	
Body Mass Index	X	
BODE Index	X	
Medication Use	X	
Residual Volume (RV)	X	
RV % Predicted	X	
Total Lung Capacity (TLC)	X	
TLC % Predicted	X	
RV/TLC	X	
IC/TLC	X	
Vital Capacity	X	
Forced Vital Capacity (FVC)	X	
FVC % Predicted	X	
FEV ₁	X	
FEV ₁ % Predicted	X	
FEV ₁ / FVC	X	
Lobar Volume	Х	
Lobar Destruction Scores	Х	
Ipsilateral DS Heterogeneity	X	
Severity of emphysema (GOLD classification)	X	
Comorbidities	X	
Target Treatment Lobe		Х
Treatment Group		Х

VI. Secondary Valve Procedures

Secondary valve procedures will be evaluated by examining the proportion of patients who undergo valve removal, valve replacement, or valve adjustment, and describing the reasons they occurred. Data for these study participants will be contrasted to data for study participants who did not receive a secondary valve procedure.

VII. Safety Analyses

Evaluation of the short- and long-term adverse events profile during the treatment period, defined as the day of the study procedure until 45 days after the study procedure (short), and in the post-treatment period, defined as 46 days after the study procedure until the 1-year follow-up visit (long). For the Control arm, the date of study procedure will be considered the date of the bronchoscopy assessment. Safety analyses will be performed by examining the percentage of patients that experiences adverse events. The rates and 95% exact confidence intervals will be presented on an event and on a per-patient basis. The percentage of subjects reporting adverse events occurring in at least 3% of subjects in either treatment arm will be compared using a Fisher's Exact test.

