Adverse events will be categorized into clinically relevant groups (*e.g.:* stable pneumothorax with no intervention, pneumothorax resolved with chest tube insertion in less than 7 days,

prolonged air leak, etc.). Adverse events occurring in the treatment arm will be further categorized by severity and as device-related, procedure-related, or neither, and by those occurring during procedure hospitalization and those occurring post-discharge.

Rehospitalization rates will be reported by study arm on a Per-Patient (PPt) basis and on a Per-Event (PE) basis. In study participants who receive EBV treatment, adverse events will be evaluated by stratifying participants by use of conscious sedation and general anesthesia during the bronchoscopy procedure as well as evaluating number of valves received and sites EBV were placed.

VIII. Mortality

A Kaplan-Meier survival curve for each study arm will graphically display the time to death from the time of randomization and a log rank test will be used to compare Kaplan-Meier curves between study arms. A Cox proportional hazards model will be used to control for study site along with other significant co-variates as applicable.

IX. Patient Accountability and Missing Data

Every effort will be made to collect all data points in the study. The sponsor plans to minimize the amount of missing data by appropriate management of the prospective clinical trial, proper screening of study subjects, and training of participating investigators, monitors and study coordinators.

- The analysis for the primary endpoint will be performed by imputing missing data. Subject death prior to the 1-year visit date will be imputed as failure.
- For study participant FEV₁ data that is 'intermittent', missing outcomes will be imputed by linear interpolation using the FEV₁ value from the latest non-missing data point before the missed data point and the earliest non-missed data point after the missed data point.

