Table 7. Effectiveness Endpoints for Control Arm Crossovers (comparison based on paired Control versus EBV Treatment differences)

The time-course of outcomes will be described. A paired t-test will be used to test the difference between treatment modalities for the quantitative outcomes. For binary outcomes, a McNemar test will be used to test the difference between the two treatment modalities.

b. Safety Outcomes

Evaluation of the short- and long-term adverse events profile of crossed-over participants during the second year of follow-up, when they have the EBV treatment, will be assessed as in Section VII above. Additionally, the time-course of occurrence of Serious Adverse Events (SAEs) will be contrasted and compared for the first year (Control Treatment) versus second year (EBV Treatment) periods. For those SAEs that could occur with either Control or EBV Treatment, a McNemar test-statistic will be used to quantify the magnitude of the difference between the two treatment modalities.

XI. Randomization Assignment Method

Study participants who are determined to meet screening, baseline, and procedure eligibility criteria will be randomly assigned to Study Treatment (EBV or Control). Random assignment will be performed using a stratified permuted block design, generated separately for each clinical site, with assignment stratified by anatomical site of the planned treatment (e.g. right lung or left lung). Mixed block sizes will be used.

XIII. Device Malfunction Analyses

Results of any device malfunctions and their sequelae are to be presented descriptively. The rate and exact 95% confidence intervals will be computed.

XIV. Statistical Software

The parametric and non-parametric analysis of variance and other primary analyses will be done using SAS, Version 9.2 or later or StatXact.

References

- 1. Meinert, C. (1986). *Clinical Trials: Design, Conduct, and Analysis*. Oxford University Press, New York.
- 2. Medical Devices Dispute Resolution Panel Meeting of September 6, 2001 (Panel Transcript)
- 3. Hochberg (1988) A sharper Bonferroni procedure for multiple tests of significance. Biometrika 75(4):800-802

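### The SAP breaks adverse events down by severity in the EBV arm only, so the severe-event percentage would be reported with no control figure

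*SAP*

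**What the plan says.** The protocol's Study Purpose (section 4.0) is to assess safety and effectiveness "in treated study participants compared to control participants". Section 21.1 lists severity (mild, moderate or severe) among the items recorded for each adverse event and limits it to neither arm: "Collection of adverse event data will commence upon random assignment of a study participant".

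SAP section VII plans the following:

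- The percentage of patients with adverse events, with exact 95% intervals per event and per patient, in a short period (procedure day to day 45) and a long period (day 46 to the 1-year visit). For controls the clock starts at the assessment bronchoscopy.
- A between-arm test by event type: "adverse events occurring in at least 3% of subjects in either treatment arm will be compared using a Fisher's Exact test".
- A severity and relatedness breakdown: "Adverse events occurring in the treatment arm will be further categorized by severity and as device-related, procedure-related, or neither". The same sentence goes on to separate events during the procedure hospitalisation from those after discharge.
- Rehospitalisation: "Rehospitalization rates will be reported by study arm on a Per-Patient (PPt) basis and on a Per-Event (PE) basis".

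Section VIII compares mortality between arms by log-rank test, with a Cox model. The only analysis that names SAEs is in section X.b, for controls who crossed over: "the time-course of occurrence of Serious Adverse Events (SAEs) will be contrasted and compared for the first year" against the second, after EBV treatment.

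**The concern.** A severe-event percentage in one arm cannot be interpreted alone in this disease. COPD exacerbation and pneumonia also occur under medical management, so part of any EBV figure is background. The control figure shows how much. Protocol section 15.1 makes a prediction that needs both arms: higher event rates with EBV up to day 45, then similar rates. The SAP's change history gives between-arm comparison in both periods as the reason for revising the safety endpoint. A one-arm severity table cannot serve that aim.

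The crossover analysis of SAEs does not fill the gap. Protocol section 7.5 says that to qualify, "a control arm participant must have been followed up successfully through 1 year and demonstrate lack of a clinically important response". That is a selected subset compared with itself over time, not a comparison of randomised arms.

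**Working it through.** The plan gives no figure to reproduce. The check is a reading of the text, followed by an illustration.

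**1. Does 'the treatment arm' mean EBV only?** Yes. The sentence also covers device relatedness and the procedure hospitalisation, and the Fisher sentence in the same section writes 'either treatment arm' when both are meant.

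**2. Is a by-arm severity or SAE summary named elsewhere?** The protocol's safety, oversight, analysis and reporting sections (15 and 19 to 21), Appendix 19, and SAP sections I, III, VII, VIII and X name none.

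**3. What is already covered by arm?**

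| Component | Planned by arm? |
|---|---|
| Death | Yes: log-rank and Cox (SAP VIII) |
| Rehospitalisation | Yes: per patient and per event (SAP VII) |
| Event types at 3% or more in either arm | Yes: Fisher's exact test (SAP VII) |
| Health care utilisation, including emergency visits and respiratory admissions | Yes: descriptive (SAP IV.C.b; protocol 13.2.7) |
| Severity grade | EBV only |
| At least one SAE | Not named; not excluded |

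For the index stay, protocol section 21.2 counts as serious an event that "Requires inpatient hospitalization or prolongation of existing hospitalization". Section 11.6 requires EBV participants to stay at least 5 nights. An event that prolongs that stay is an SAE but not a rehospitalisation. It still enters the short-period rates and, if its type reaches 3%, the Fisher test, and it is shown in the EBV split by procedure hospitalisation. What it lacks is a seriousness flag and a matching control figure.

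**4. What the missing control column could hide.** Inputs:

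- 190 enrolled (SAP, Study Design) at 2:1 (protocol 8.9.1). 190 × 2/3 = 126.7, so 127 v 63 is assumed.
- All event counts are assumed.

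EBV row: 32/127 = 25.2%, exact (Clopper-Pearson) 95% CI 17.9 to 33.7.

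Difference d = p1 - p2 with Newcombe limits built from the Wilson limits (l, u) of each arm:

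- lower = d - √[(p1 - l1)² + (u2 - p2)²]
- upper = d + √[(u1 - p1)² + (p2 - l2)²]

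For 32/127 v 5/63: p1 = 0.2520, Wilson 0.1845 to 0.3340; p2 = 0.0794, Wilson 0.0344 to 0.1727; d = 0.1726.

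- Lower = 0.1726 - √(0.0675² + 0.0933²) = 0.057
- Upper = 0.1726 + √(0.0820² + 0.0450²) = 0.266

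| Controls with a severe event (assumed) | EBV minus control, points | 95% CI |
|---|---|---|
| 5/63 (7.9%) | +17.3 | 5.7 to 26.6 |
| 9/63 (14.3%) | +10.9 | -1.7 to 21.4 |
| 13/63 (20.6%) | +4.6 | -8.8 to 16.1 |
| 16/63 (25.4%) | -0.2 | -13.9 to 12.1 |

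The severity row planned in the SAP would read 25.2% in all four cases.

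**The case against.** The best reply is that the plan already shows most of the serious burden by arm and that a table not named is not a table forbidden. For SAEs this largely stands. The general sentence on rates in SAP VII leaves room for a by-arm SAE percentage, SAEs are collected without an arm limit, and the Clinical Events Committee adjudicates all serious events. Section 15.1 also lists event types defined by their consequence, such as pneumothorax requiring intervention, which can be compared between arms if they reach 3%. After discharge, the SAEs outside both death and rehospitalisation are non-fatal life-threatening or disabling events without admission. Nothing in the documents suggests there would be many.

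A reader might infer that serious events during the EBV index stay go unreported, or that the plan gives no by-arm view of serious harm. The documents support neither, as the coverage table shows.

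The reply does not reach severity. There the SAP is not silent: it states a rule for one arm.

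A second objection also stands: early detection is unequal. EBV participants have the required inpatient stay with daily assessment, 10 days of calls after discharge, and day-7 and day-30 visits that controls do not have (protocol 8.10.2, 11.6 and 14.6 to 14.8). A short-period difference in severe events would therefore mix treatment effect with closer observation. That calls for a caveat beside the control figure, not for leaving the figure out.

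**Conclusion.** The concern holds for severity: the written rule yields an EBV-only table, at odds with the trial's comparative purpose and the stated aim of the revised SAP. For SAEs it holds only as an unnamed summary, since the underlying events are collected and many are already compared by arm. The point is minor. It is a gap in the pre-specified tables and touches no endpoint, success criterion or data collection.

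The size cannot be taken from the documents. The illustration rests on the assumed split and assumed counts, and shows only that the same EBV row fits anything from a large excess to none.

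**What to change.** In SAP section VII, categorise adverse events by severity in each arm and keep device relatedness for EBV only. For the short and long periods, report by arm the percentage with at least one severe adverse event and the percentage with at least one committee-adjudicated SAE. Give the between-arm difference and 95% CI for each, in both the ITT and As Treated safety populations, alongside the Fisher tests by event type and not in their place.

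Label the intervals as unadjusted for multiplicity. State that short-period differences partly reflect closer EBV follow-up: the stay of at least 5 nights, the 10 daily calls, and the day-7 and day-30 visits.

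The cost is a change of wording and a few extra tables. Severity is already on the case report form and serious events are already adjudicated, so no new data are needed.

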7.6 Interim Analysis

An interim data analysis designed to evaluate effectiveness for continuing crossover of Control arm study participants after the 1 year follow-up visit to EBV treatment will be performed when 74 (50% of the required minimum of 147) study participants have completed the 1 year follow-up. If crossover of Control arm study participants is found to be justified by the interim analysis then crossover of Control arm study participants after (s)he has reached the 1-year time point may be continued. The results of the interim analysis will be reviewed by the DSMB and FDA. If the DSMB recommends not continuing crossing control arm participants to EBV treatment, then those control arm participants who have not crossed over will exit from the study protocol after the 1-year visit.

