7.7 Long-Term Follow-Up

Data will be collected annually through 5 years for study participants receiving the study treatment. Per the regulatory plan agreed to with FDA, 1 year of follow-up is required pre-approval and the remaining 4 years of follow-up will be conducted post-approval. The annual 2-, 3-, 4-, and 5-year follow-up data will consist of FEV₁ and adverse events.

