14.14 Annual Visits (+/- 60) only for Study Participants treated with EBV

- Spirometry
- Adverse Event Assessment

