Appendix 12. Required Schedule for Follow Up Tests and Procedures CONTROL Subjects

TESTING	Day 0 - Bronchoscopy	45 Days	3 Months	6 Months	9 Months	1 Year	ET/EWD
LUNG FUNCTION TESTING							
Spirometry		X		X		X	X
Body Plethysmography		X				X	
Diffusing Capacity		X				X	
EXERCISE TOLERANCE							
Six-Minute Walk Test		X		X		X	
BASIC MEDICAL							
Vital Signs / Physical Exam	X	X	X	X		X	X
Review of Medications		X	X	X	X	X	X
Electrocardiography						X	
Pulse Oximetry	X						
BLOOD WORK							
Arterial Blood Gases (ABGs)	X					X	
Complete Blood Counts (CBCs)						X	
Plasma Cotinine or Arterial Carboxyhemoglobin						X	
Serum Fibrinogen	X					X	
MEDICAL MANAGEMENT							
Pulmonary Rehabilitation*	X						
HEALTH SURVEYS							
SGRQ			X	X		X	
MMRC		X		X		X	
BDI/TDI			X	X	X	X	
CAT			X	X	X	X	
SF-36						X	
EQ-5D						X	
Health Care Utilization			X	X	X	X	
DAILY DIARY**							
PR Program Compliance		X	X	X	X	X	
Exact-PRO		X	X	X	X	X	
Health Status Change		X	X	X	X	X	
SAFETY							
Adverse Events	X	X	X	X	X	X	X

*starts within 30 days after bronchoscopy procedure; **daily diary recording to begin Day 1 after Bronchoscopy through 1 year follow up visit

LIBERATE Study Clinical Investigation Plan #630-0012-H

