- For study participants with truncated data (e.g. participants who drop out or are lost to follow-up), a multiple imputation strategy will be performed using the propensity score method. In brief, for a particular outcome, the propensities for study participants to have missing data (for each treatment group separately), modeled by logistic regression, are grouped into strata based on percentiles of the logistic propensity score model. Within a stratum, a study participant with a missing observation has an imputed value assigned by randomly choosing a value from among the study participants in the same stratum with non-missing observations. This procedure will be repeated 20 times on the entire dataset, resulting in 20 different 'complete' datasets allowing for estimation of the effect on the outcome of interest, accounting for missing data.

An additional analysis for the primary endpoint will be performed based on not imputing data. All partial data that is available on subjects who drop out during the course of the study will be included. In addition, sensitivity analyses such as worse-case or best-case imputation will be performed although it is recognized that they are biased.

Missing data for secondary endpoints will be imputed using the same methodology described above. Subject death prior to the 1-year visit date will be imputed baseline carried forward (0-point change).

- X. Comparison of Crossed-Over Control versus Study Treatment Outcomes
 - a. Effectiveness Outcomes

omparison based on paired Control versus EBV Treatment differences)				
Variable	Unit	Values Statistically Evaluated		
Forced Expiratory Volume (FEV ₁)	>15% improved	percentage of participants		
FEV ₁	Liters	mean absolute change		
FEV ₁	percent	mean percent change		
SGRQ Total Score	Points	mean absolute change		
mMRC Score	semi-quantitative	mean absolute change		
	scale score			
6-Minute Walk Distance	Meters	mean absolute change		
6MWD – subjects stratified by	meters	mean absolute change		
distance walked at baseline				
6MWD	25 meters	percentage of participants		
	improved			
DLco	percentage	mean absolute and percent change		
Residual Volume (RV)	liters	mean absolute and percent change		
Inspiratory Capacity (IC)	liters	mean absolute and percent change		
Total Lung Capacity (TLC)	liters	mean absolute and percent change		
RV/TLC	ratio	mean absolute change		
IC/TLC	ratio	mean absolute change		

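### SAP IX puts no time limit on FEV₁ interpolation, so a missed 1-year primary outcome can be filled with 2-year data in EBV-treated participants but normally goes to multiple imputation in controls

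*SAP*

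**What the plan says.** SAP section IX (Patient Accountability and Missing Data) has two rules for a missing FEV₁ in a participant who has not died.

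- *Intermittent* data: linear interpolation between "the latest non-missing data point before the missed data point and the earliest non-missed data point after the missed data point". No latest permissible date is given for the second point.
- *Truncated* data (dropout, loss to follow-up): "a multiple imputation strategy will be performed using the propensity score method", with propensities modelled separately by arm and 20 completed datasets.

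For the other endpoints, "Missing data for secondary endpoints will be imputed using the same methodology described above". Death before the 1-year visit counts as failure for the primary endpoint and as zero change for the secondary endpoints.

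The schedules differ by arm after 1 year. The Protocol Appendix 12 table headed "Required Schedule for Follow Up Tests and Procedures CONTROL Subjects" has spirometry at 45 days, 6 months, 1 year and early termination or withdrawal. The treated table has the same visits plus years 2 to 5. Section 14.14 holds annual visits "only for Study Participants treated with EBV", and section 7.7 says "Data will be collected annually through 5 years for study participants receiving the study treatment". Neither arm has spirometry scheduled between 6 months and 1 year.

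Controls may cross over after the 1-year visit (section 7.5), and then "the follow-up visits and testing at each visit will be identical to the study schedule for treatment arm participants". If the DSMB advises against further crossover, section 7.6 says "those control arm participants who have not crossed over will exit from the study protocol after the 1-year visit".

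**The concern.** Responder status uses only baseline and 1-year FEV₁. Because 1 year is the last visit the two arms share, a missing 1-year value can be intermittent only if a later value exists. By schedule, such a value exists for EBV-treated participants and not for untreated controls.

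The same gap in the primary outcome is therefore filled by two different methods. In the EBV arm it can become a single interpolated number, treated as if observed. In the control arm it is normally drawn 20 times from participants in the same propensity stratum, so the imputation uncertainty is carried through. Within the EBV arm the method depends on having enrolled early enough to reach year 2 before the data cut, and on attending that visit. Both are facts from after the outcome date, and the SAP fixes no cut date. Two analysts following the SAP could reach different 1-year responder counts.

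**Working it through.** **Plan figures used.** The interpolation rule carries no figure of its own. The figures borrowed below are 35% and 10% responders (Protocol 20.3.1), 190 enrolled, and a final critical value of 2.004 (SAP IV.A). The critical value reproduces: 0.05 × 0.5^2.3 = 0.01015 is spent at the interim look, which gives bounds of 2.5706 and 2.0036.

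**Interpolation weights, EBV participant with 6-month and 2-year values.** The weight on the 2-year value is (12 − 6)/(24 − 6) = 1/3, leaving 2/3 on the 6-month value. Using actual days at the edges of the visit windows:

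- (365 − 161)/(790 − 161) = 0.32
- (365 − 203)/(670 − 203) = 0.35

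If the 6-month value is also missing, the 45-day to 2-year weight is (365 − 45)/(730 − 45) = 0.47. Baseline is common to all points, so these weights apply equally to percentage change.

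**What this does to responder status.** With +20% at 6 months, the imputed value reaches 15% when the 2-year change is at least 3 × (15 − 2/3 × 20) = +5%. The error can go either way (hypothetical participants):

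| 6 months | True 1 year | 2 years | Imputed 1 year | Effect |
|---|---|---|---|---|
| +20% | +12% | +8% | 2/3 × 20 + 1/3 × 8 = 16.0% | non-responder counted as responder |
| +20% | +16% | +2% | 2/3 × 20 + 1/3 × 2 = 14.0% | responder counted as non-responder |

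**How many could be affected.** The documents do not say, so this is an illustration. At the planned 15 per month, 183 participants take 183/15 = 12.2 months (Protocol 23.1). The last 1-year window closes at about 12.2 + 12 + 1.5 = 25.7 months. Suppose the data are cut then.

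- Participants enrolled in the first 1.7 months have reached a nominal 2-year visit: 1.7 × 15 ≈ 25, of whom 2/3 ≈ 17 are EBV.
- If 2-year visits fall at the early edge of their window (60 days, about 2 months), this becomes the first 3.7 months: about 55, of whom 37 are EBV.
- If 5% to 10% of these miss the 1-year test but attend year 2 (assumed), 17 × 0.05 ≈ 1 to 37 × 0.10 ≈ 4 participants are interpolated.

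Slower accrual or a later cut raises the count. Only those near the 15% threshold can change status.

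**Effect on the primary test.** Assume 127/63 from 2:1 allocation of 190, and the planned rates, so 44.45 and 6.3 expected responders. The pooled rate is 50.75/190 = 0.267, and Z = 0.25/√(0.267 × 0.733 × (1/127 + 1/63)) = 3.67.

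| Change | Z |
|---|---|
| None | 3.67 |
| 5 fewer EBV responders | 3.20 |
| 5 more EBV responders | 4.12 |

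One EBV participant moves the arm's rate by 1/127 = 0.8 points.

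**Crossover edge case.** A control whose 1-year visit was held but whose FEV₁ was unusable, and who crossed over 0 to 60 days later, next has spirometry at about day 410 to 470. The weight on that post-EBV value would be (365 − 182)/(410 − 182) = 0.80 down to (365 − 182)/(470 − 182) = 0.64. With no change at 6 months, a post-EBV gain of about 19% to 24% would make that control a responder.

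**The case against.** The best defence is that the primary evaluation is at 1 year, that years 2 to 5 are post-approval follow-up, and that with 12-month recruitment few 2-year values would exist at the analysis. The SAP also requires an analysis without imputation, best- and worst-case imputation, a completed-cases analysis and a within-window per-protocol analysis, any of which could expose dependence on the rule. All of this is fair, and it limits the size of the problem. It does not settle which value the primary analysis uses.

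Three stronger readings are tempting, and the documents do not support them.

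- *EBV responders are over-counted.* That needs the effect to wane early, between 6 months and 1 year. If it holds to 1 year and fades later, the rule under-counts, as the second example shows.
- *Control outcomes are built from device effects.* Protocol 7.5 and 14.13 require successful follow-up through 1 year before crossover, so this needs an unusable 1-year test or a deviation. The SAP does not exclude such values, but the case is nearly empty.
- *A control's only possible later value is post-crossover.* Early-termination or withdrawal spirometry (8.11.1, Appendix 12) or a late out-of-window 1-year test (8.10.2) could supply an untreated one. The SAP does not say whether an out-of-window test counts as missing in the ITT analysis.

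**Conclusion.** The point stands as a flaw in a stated rule. Followed as written, SAP IX handles a missing 1-year primary outcome differently by arm and, in the EBV arm, by data-cut date and year-2 attendance. The secondary FEV₁ change inherits this. The 2-year route does not reach 6MWD or SGRQ, which are not scheduled in years 2 to 5.

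The likely effect is small. The illustration of 1 to 4 interpolated participants rests on planned accrual, a cut at the close of the last 1-year window and an assumed 5% to 10% missing rate. At the planned rates and an assumed 127/63 split, moving five EBV responders leaves Z between 3.20 and 4.12 against 2.004. A reader might infer that the trial's conclusion is at risk; on the planning figures it probably is not, though a smaller true difference would leave less room. The direction of bias is not determined. The change is still worth making, because it removes an arm-dependent choice from the primary analysis at almost no cost.

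**What to change.** Add two statements to SAP IX.

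1. No FEV₁ value obtained after the end of the 1-year window, and no value of any endpoint obtained after crossover, may be used to fill a 1-year outcome. Interpolation of FEV₁ then applies only to missed 45-day and 6-month values.
2. A missing 1-year value is handled by the same propensity-score multiple imputation in both arms. Deaths stay as the SAP has them: failure for the primary endpoint, zero change for the secondary endpoints.

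The same edit should say whether a late, out-of-window 1-year test counts as the observed 1-year value in the ITT analysis, so that the first statement does not decide this by accident.

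The cost is a short SAP amendment, with no new data and no change to the sample size of 147. A few EBV participants who have 2-year data would be multiply imputed instead of interpolated, which slightly widens the interval.
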